1.1. Introduction

As the population of persons living with HIV ages in the United States, lung cancer is now the leading cause of cancer death, with risk related to both increased tobacco use as well as independent risk associated with chronic HIV infection. Lung cancer screening with annual low-dose chest CT has been demonstrated to reduce lung cancer mortality by up to 20% in a subset of high-risk smokers, though potential longitudinal benefits may be greatly reduced in those with comorbid illness. While lung cancer screening is both feasible and likely highly beneficial in many persons living with HIV, there are limited prospective data and no HIV-specific guidelines to support tailored lung cancer screening decision making in this population, who are at higher risk for multimorbidity associated with aging. This study will bridge this significant knowledge gap through the iterative development and evaluation of tools to guide the shared decision making process for lung cancer screening in persons living with HIV. The study will consist of the following specific aims and approach: 1) Conduct a formative evaluation using qualitative methods to guide adaption and implementation of shared decision making for lung cancer screening tailored to persons living with HIV incorporating lung cancer risk as well as HIV severity, comorbidity and life expectancy; and 2) Pilot and evaluate tailored shared decision making using mixed-methods to assess the impact on patient knowledge and decisional conflict, as well as intervention acceptability, appropriateness and fidelity. Aim 1 includes focus groups of persons living with HIV and interviews with their primary providers to determine key barriers and facilitators to tailored shared decision making. Measures of comorbidity and life expectancy are also incorporated into this process to develop a tailored shared decision making intervention. Aim 2 is a single-arm feasibility trial to determine both the preliminary effectiveness and implementation of the shared decision making approach. The results of this study will be used to develop and refine tools for shared decision making for lung cancer screening in persons living with HIV, allowing for subsequent scale-up of implementation and assessment of effectiveness, reach and sustainability in a multicenter trial. This study directly addresses NIH high priority research topics of malignancy and comorbidity associated with HIV.

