2.1. Aims

Aim 1. Conduct a formative evaluation using qualitative methods to guide adaption and implementation of shared decision making (SDM) for LCS tailored to PWH incorporating lung cancer risk as well as HIV severity, comorbidity and life expectancy.

H1. Key themes will emerge from focus groups and interviews with PWH and providers that will help structure a SDM process for PWH and determine how best to incorporate measures of HIV severity, comorbidity and life expectancy, such as the Veterans Affairs Aging Cohort Study and Charlson Comorbidity risk indices.

Aim 2. Pilot and evaluate tailored SDM using mixed-methods to assess the impact on patient knowledge and decisional conflict, as well as intervention acceptability, appropriateness and fidelity.

H2. Tailored SDM will result in improvements in patient knowledge and result in low levels of decisional conflict. Surveys of patients and interviews of patients and stakeholders will be utilized to inform and subsequently iterate the intervention with regards to acceptability, appropriateness and fidelity.

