2.3. Study Duration, Enrollment and Number of Sites

2.3.1. Date Range of Study

This study will be conducted October 2020-September 2022. Estimate to complete Aim 1 in months 1-10 and Aim 2 in months 11-24.

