2.4. Study Population

2.4.1. Inclusion Criteria

Aim 1. We will recruit participants from two groups: PWH enrolled in the local UW HIV cohort and primary providers at Madison Clinic and other Seattle-based clinics serving PWH. Using proposed USPSTF guidelines, participants enrolled in the registry who are current or former smokers, ≥ 50 years old, and report ≥ 20 pack-years smoking history (n=165) will be eligible for recruitment. A purposive sample will be recruited, making every effort to include patients of diverse race/ethnicity, sex, income, and spanning the eligible age range for LCS. We will pay particular attention to recruiting women as well as men. Clinicians (medical doctors, physicians assistants, and nurse practitioners) who provide primary care for PWH (n=48) will be eligible.

Aim 2:

PWH who are eligible for LCS based on current USPSTF criteria^[SMA1]. Plan to enroll approximately 50% who have never had a lung cancer screening exam, and 50% who are overdue (~12 months) for lung cancer screening exam.

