3.2.2. Shared Decision Making visit

The coordinator will administer a pre-SDM survey that includes participant demographics, participant-reported risk factors, tobacco history, an assessment of LCS knowledge (the LKS) used in our prior study³⁶ and minimalist/maximalist approach to healthcare⁴⁰ (Addendum 8.1). Participants will then meet with the LCS nurse practitioner (NP), who will provide the SDM intervention and will supplement the discussion using language regarding comorbidity and life expectancy developed in Aim 1 to frame decisions; they will come to a mutual decision on whether to move forward with the screening process. To inform the tailored discussion, comorbidity burden and life expectancy will be estimated for each participant prior to the visit, using data from the UW HIV Information System (UWHIS) and EPIC to generate CCI, LCRAT, LCDRAT and VACS 2.0 Index from electronic-health records data (ICD-10 codes and most recent lab values within 1 year). A HIPAA waiver has been requested for this purpose. Prior to the visit, the participants lung cancer risk will be calculated using the LCRAT and the LCDRAT tools and mortality risk will be calculated using the VACS Index 2.0. The NP will receive an interpretation of these results, based on published literature and our preliminary work to guide discussion. The NP will complete SDM with the patient using the tailored SDM tool (Addendum 19) and guide (Addendum 20). The coordinator will observe the SDM discussions in order to complete an observational checklist assessing fidelity of the intervention (Addendum 9). Participants will then complete a post-SDM survey re-assessing LCS knowledge, resultant decisional conflict using the low literacy decisional conflict scale,³⁷ as well as validated quantitative 4-item scales of acceptability and appropriateness developed by Co-I [name], the Acceptability of Intervention Measure (AIM) and the Intervention Appropriateness Measure (IAM)(Addendum 8.2)³⁸ Participants who go on to LCS will be enrolled in the LCS program and linked to screening by a patient navigator.

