3.2.5. Sample Size

As this is a feasibility study and the majority of our outcomes are summarized, there is no appropriate power calculation to determine sample size. In our previous study of pre- and post-SDM knowledge, we found an improvement in overall understanding of possible harms of lung cancer screening from 69% to 93% in a group of 45 patients ($p=0.002$), and relatively few patients would need to be enrolled to demonstrate that magnitude of change. However, because we are interested in a robust sample to assess the other outcomes, we plan to enroll at least 50 patients into the SDM intervention. We will then sample patients for interviews until thematic saturation on acceptability and appropriateness are reached.

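### Aim 2 promises the impact on decisional conflict, but the scale is listed only after the visit, so no change in conflict can be estimated

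*Combined protocol and SAP*

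**What the plan says.** Section 1.1 describes the design: "Aim 2 is a single-arm feasibility trial to determine both the preliminary effectiveness and implementation of the shared decision making approach". Section 2.1 gives the purpose of Aim 2 as "to assess the impact on patient knowledge and decisional conflict". The hypothesis beneath it treats the two outcomes differently: "Tailored SDM will result in improvements in patient knowledge and result in low levels of decisional conflict".

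Section 3.2.2 sets out the two surveys.

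- **Before the visit:** "The coordinator will administer a pre-SDM survey that includes participant demographics, participant-reported risk factors, tobacco history, an assessment of LCS knowledge", followed by a measure of the participant's minimalist or maximalist approach to care. The decisional conflict scale (DCS) is not listed.
- **After the visit:** "Participants will then complete a post-SDM survey re-assessing LCS knowledge, resultant decisional conflict using the low literacy decisional conflict scale", together with the acceptability and appropriateness scales.

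Section 3.2.6 plans a before-and-after test for the knowledge responses. For the DCS it plans only a median on the 0-100 scale, where higher means more uncertainty.

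On sample size, section 3.2.5 gives no power calculation and says "because we are interested in a robust sample to assess the other outcomes, we plan to enroll at least 50 patients".

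**The concern.** With one arm there is no between-group contrast, so any statement about impact has to rest on change from each participant's own starting point. The plan provides that for knowledge and not for conflict, although Aim 2 names both.

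A low score after the visit has two readings: conflict fell during the visit, or it was already low on arrival. The planned data cannot separate them. The second reading cannot be dismissed, because section 2.4.1 plans to enrol "approximately 50% who have never had a lung cancer screening exam, and 50% who are overdue". Overdue participants may have met this decision before. That is an inference, since the documents give no baseline conflict data.

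At stake is half of Aim 2's effectiveness statement. A report of impact on conflict would have no estimate behind it, and the later multicenter trial foreseen in section 1.1 would inherit no SD of change for this outcome.

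**Working it through.** **1. What is measured, outcome by outcome.**

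| | Knowledge (LKS) | Decisional conflict (DCS) |
|---|---|---|
| Aim 2 (2.1) | impact | impact |
| H2 (2.1) | improvement | low level |
| Pre-SDM survey (3.2.2) | listed | not listed |
| Post-SDM survey (3.2.2) | listed | listed |
| Analysis (3.2.6) | pre/post test | median of one set of scores |
| Planned pairs, of at least 50 | all | 0 |

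The plan states no figure for change in the DCS, so there is none to reproduce.

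**2. What a post-visit median says about change.** Write change = post - pre. The baseline lies between 0 and 100, so each participant's change lies between post - 100 and post. The median preserves this ordering, so if the post-visit median is m, the median change lies between m - 100 and m.

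- Example: m = 20 gives 20 - 100 = -80 up to +20.
- The interval includes both signs for every m strictly between 0 and 100. Only at the ends is one direction excluded (at m = 0 the median change cannot be positive; at m = 100 it cannot be negative).
- The width is 100 points and does not depend on n, so enrolling more participants does not help.

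**3. What a baseline would buy.** For the Hodges-Lehmann estimate of paired change with roughly normal differences, the 95% half-width in units of the SD of the differences is about

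t(0.975, n-1) / sqrt(n) x sqrt(pi/3),

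where sqrt(pi/3) = 1.023 is the cost of the rank-based estimate relative to the mean.

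- n = 50: 2.010 / 7.071 x 1.023 = 0.291
- n = 45: 2.015 / 6.708 x 1.023 = 0.307
- n = 25: 2.064 / 5.000 x 1.023 = 0.422

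A simulation of the interval (3,000 runs each) gave 0.291, 0.308 and 0.426.

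The documents give no SD for the DCS. For assumed SDs of the differences:

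| Pairs | SD 15 | SD 20 | SD 25 |
|---|---|---|---|
| 50 | 4.4 | 5.8 | 7.3 |
| 45 | 4.6 | 6.1 | 7.7 |
| 25 | 6.3 | 8.4 | 10.6 |

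Entries are half-widths in points. The 45 stands for some incomplete pairs and the 25 for a baseline added when half are already enrolled; both are assumptions.

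**4. A wider range of assumptions.** Suppose instead that 15 to 25 is the SD of a single score and the pre/post correlation r is 0.3 to 0.7. Then SD of change = SD x sqrt(2(1 - r)), which runs from 15 x sqrt(0.6) = 11.6 to 25 x sqrt(1.4) = 29.6. With 50 pairs, the t-interval half-width for the mean change is 3.3 to 8.4 points.

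**The case against.** The strongest reply is that the working parts of the plan agree with one another. H2 predicts improvement for knowledge but only low levels for conflict, section 3.2.2 presents the DCS as an outcome of the visit, and section 3.2.6 plans a median. Section 3.2.5 says most outcomes are only to be summarised, as suits a feasibility study. On this view the post-only DCS was chosen, and the only fault is one word in Aim 2. That much is right about H2. It does not rescue the aim, which makes the same promise for both outcomes, nor the introduction, which speaks of preliminary effectiveness.

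A second reply is that a before-and-after change in one arm does not establish impact either. It cannot separate the tailored content from ordinary SDM, completing the scale beforehand may prime answers, and a baseline score may mean different things in never-screened and overdue participants. All of this stands and belongs in the limitations. The same limits on causation apply to the knowledge comparison the plan already makes, and a paired change is still more informative than none.

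Third, being overdue could reflect unresolved ambivalence, and so higher conflict on arrival. That is fair. The finding does not depend on which way baseline conflict lies, only on its being unmeasured.

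Finally, the pre-SDM form (Addendum 8.1) was not available for review and might contain the scale. Section 3.2.2 itemises the survey without it, and section 3.2.6 plans no DCS comparison, so the analysis text would need editing in either case.

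**Conclusion.** The concern holds. As written, the plan gives no estimate of change in decisional conflict and has no comparator that could stand in for one. Aim 2's impact on conflict therefore cannot be addressed, and except at the extremes of the scale not even its direction is identified. H2's narrower prediction of a low level is compatible with the post-only score.

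This should be corrected, but it does not threaten the study as a whole: knowledge, acceptability, appropriateness and fidelity are unaffected. The conclusion rests on the survey contents listed in section 3.2.2 and the analysis in section 3.2.6. The precision figures describe the remedy, and their SDs, correlations and numbers of pairs are assumed.

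**What to change.** **Preferred.** Add the same low-literacy DCS to the pre-SDM survey (section 3.2.2 and Addendum 8.1). In section 3.2.6, report the paired post-minus-pre change with a Wilcoxon signed-rank test, the Hodges-Lehmann estimate and its 95% interval, beside the post-SDM median and IQR. State that a single-arm change does not prove causation and does not isolate the tailored content.

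**If a baseline cannot be added.** Reword Aim 2 to the post-SDM level of decisional conflict and make no claim of impact on it.

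**If it is added part-way.** Section 2.3.1 says "Estimate to complete Aim 1 in months 1-10 and Aim 2 in months 11-24", and enrolment status is not given. A baseline helps only participants not yet enrolled. Report the change in those with both scores and the post-SDM level in everyone.

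A secondary text edit is to state before analysis which score counts as low for H2.

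**Cost.** One short scale in a survey already given at the same visit: a few minutes of respondent time, possible priming, and a pooled change that may mix different meanings of baseline conflict in never-screened and overdue participants, to be stated as a limitation. Rewording the aim and defining low cost only text.

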3.2.3. Post-intervention interviews

Approx. 5 weeks post-SDM, 10-15 purposefully selected participants chosen to represent both broad demographics and maximum variation on AIM and IAM scores will be contacted for a 45-minute telephone or HIPAA-approved ZOOM interview to explore factors that might influence intervention acceptability and appropriateness. These will be conducted by the RC. Similar interviews will be conducted with the NP. Interview guides (Addenda 10, 11, 12) will be adapted throughout Aim 2 to better capture participant perspectives. The NP interview will also explore factors that might influence fidelity of intervention delivery. All interviews will be recorded and transcribed. This will have separate consent delivered over the phone by RC (Addendum 13.1 and 13.2).

3.2.4. Review of EHR.

Participants in Aim 2 will provide consent and HIPAA authorization (Addendum 14) for limited review of their medical records at the time of clinical visit. A HIPAA waiver has been requested

for review of EHR prior to clinical visit to determine comorbidity burden and life expectancy measures used in production of a tailored SDM tool. The EHR will be assessed for participants to determine the following information post-SDM visit: data of lung cancer screening scheduling, documentation of patient encounters around lung cancer screening, lung cancer screening results, lung cancer screening follow-up screening, procedures, and patient visits.

3.2.5. Sample Size

As this is a feasibility study and the majority of our outcomes are summarized, there is no appropriate power calculation to determine sample size. In our previous study of pre- and post-SDM knowledge, we found an improvement in overall understanding of possible harms of lung cancer screening from 69% to 93% in a group of 45 patients ($p=0.002$), and relatively few patients would need to be enrolled to demonstrate that magnitude of change. However, because we are interested in a robust sample to assess the other outcomes, we plan to enroll at least 50 patients into the SDM intervention. We will then sample patients for interviews until thematic saturation on acceptability and appropriateness are reached.

3.2.6. Data Collection and Analysis

Pre-/post-SDM survey data will be collected via tablet, with a paper option if desired. Participants will directly enter data into secure Research Electronic Data Capture (REDCap, Vanderbilt University) software. All interviews will be recorded and transcribed. Key outcomes are described above. Pre- and post-intervention LKS responses will be compared via Chochran-Mantel-Haenszel or Friedman test based on data type. A Chochran-Mantel-Haenszel test will be used with categorical data and a Friedman test will be used with non-categorical data. The DCS will be summarized as the median of scores for participants from 0 (extreme certainty) to 100 (extreme uncertainty). The IAM and AIM will also be summarized and presented as range of scores from 1 (low acceptability/appropriateness) to 5 (high acceptability/appropriateness). Fidelity will be summarized as median percent of checklist items completed. Joint displays consistent with a mixed-methods convergent design will be used to analyze and interpret the data, with themes mapped onto the TICD as in Aim 1.³⁹

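### With two measurements the Friedman test named for non-categorical LKS data uses only the direction of each change, and the plan names no summary of change for the LKS (minor)

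*Combined protocol and SAP*

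**What the plan says.** Section 3.2.2 places the LKS in the survey before the shared decision making visit, and then: "Participants will then complete a post-SDM survey re-assessing LCS knowledge". No section describes a third measurement.

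Section 3.2.6 gives the analysis: "Pre- and post-intervention LKS responses will be compared via Chochran-Mantel-Haenszel or Friedman test based on data type". Categorical data go to the Cochran-Mantel-Haenszel (CMH) test, and for the rest "a Friedman test will be used with non-categorical data". Nothing further is said about how the LKS change will be reported, and the strata for the CMH test are not stated.

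Two other outcomes in the same section have a clear summary: "The DCS will be summarized as the median of scores for participants" and "Fidelity will be summarized as median percent of checklist items completed". The acceptability and appropriateness measures are to be summarised and shown as a range of scores from 1 to 5, which may describe the scale rather than a statistic. No outcome has a confidence interval.

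Section 3.2.5 plans at least 50 patients, says that no power calculation is appropriate, and cites an earlier study with a change in "overall understanding of possible harms of lung cancer screening from 69% to 93% in a group of 45 patients" (p=0.002). Section 1.1 states the purpose: "Aim 2 is a single-arm feasibility trial to determine both the preliminary effectiveness and implementation of the shared decision making approach", with the results "allowing for subsequent scale-up of implementation and assessment of effectiveness, reach and sustainability in a multicenter trial".

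**The concern.** The Friedman test is built for three or more repeated measures. With two, it keeps only the sign of each participant's change. If the LKS gives a total or percent-correct score, a gain of one item and a gain of four items then count the same, and that costs information and usually some power.

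The second gap sits beside it. Improvement in knowledge is one part of hypothesis H2 (section 2.1), and the LKS comparison is the only statistical test named in 3.2.6. A pilot meant to inform a multicenter trial needs the size of the knowledge gain and its uncertainty. The plan names a p-value method and asks for neither.

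**Working it through.** **Inputs.** Two LKS measurements per participant (3.2.2); n=50, the planned minimum (3.2.5); Friedman for non-categorical data (3.2.6). Two-sided 5% is assumed. The LKS scale, the SD of change and the expected effect are not in the documents, so every power figure below is illustrative.

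**1. The plan's own figure.** 31/45 = 68.9% and 42/45 = 93.3%, a net change of 11 patients. The discordant counts are not given. If 12 gained and 1 lost (assumed), the uncorrected McNemar statistic is (12 − 1)²/13 = 9.31, p=0.0023. This is compatible with the stated p=0.002, but other splits cannot be excluded: 11/0 to 14/3 give 0.0009 to 0.0076 uncorrected.

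**2. Friedman with two measures.** Let n₊ participants go up, n₋ go down and n₀ tie, with N = n₊ + n₋ + n₀. Within-person ranks are 1 and 2, or 1.5 each for a tie.
- Each rank sum differs from its expectation of 1.5N by ±(n₊ − n₋)/2, so the sum of squared deviations is (n₊ − n₋)²/2.
- The sum of squared ranks is 5(n₊ + n₋) + 4.5n₀. Subtracting 4.5N leaves (n₊ + n₋)/2.
- The tie-corrected statistic is the ratio, (n₊ − n₋)²/(n₊ + n₋), which is the sign statistic. The two agreed exactly in 2,000 simulated data sets.

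**3. Size of change is ignored.** Take 32 participants who gain and 18 who each lose one item. The statistic is (32 − 18)²/50 = 3.92, p=0.048, in both rows.

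| Gain per gainer | Mean change (95% CI) | Paired t p |
|---|---|---|
| 1 item | 0.28 (0.00 to 0.56) | 0.047 |
| 4 items | 2.2 (1.5 to 2.9) | <0.0001 |

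**4. Type I error.** Without ties at n=50, the cut-off 3.84 is passed when n₊ − n₋ is 14 or more in either direction (14²/50 = 3.92; 12²/50 = 2.88). Under no change that has probability 0.065. The exact sign test has size about 0.03 and gives p=0.065 for 32 against 18. With ties, in bounded item scores, the chi-square version has size 4.6% to 5.1%.

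**5. Power at n=50 (simulated).**

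| Normal changes, mean/SD | Friedman | Wilcoxon | Paired t |
|---|---|---|---|
| 0.3 | 43% | 52% | 55% |
| 0.4 | 66% | 77% | 80% |
| 0.5 | 83% | 92% | 93% |
| 0.8 | >99% | >99% | >99% |

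A short bounded score is closer to a knowledge scale. Scores of 5, 7 and 10 items were simulated with mean gains of 6 to 9 percentage points (0.19 to 0.42 SD). Across runs, Friedman lost about 2 to 10 points to Wilcoxon and 3 to 11 to paired t. If every item moved from 69% to 93% (0.9 to 1.2 SD), all three tests had about 100% power.

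Heavy tails reverse the order against t. At 0.3 to 0.5 SD the chi-square Friedman beat paired t by 5 to 18 points for Laplace changes and 6 to 15 for t with 3 df.

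**6. What an estimate would deliver.** For a score, the 95% CI for the mean paired change has half-width t(0.975, 49)/√50 = 0.284 SD of the change. In the bounded-score simulations that interval covered 94.7% to 95.3%. For a binary item, the assumed 12/1 split gives 11/45 = 24 points with standard error √(13 − 11²/45)/45 = 0.071, so a 95% CI of 10 to 38 points.

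**The case against.** The strongest reply is that the test point may apply to nothing. The plan speaks of responses, picks the test by data type, and cites an earlier result that is a percentage. That suggests, without proving, that the LKS is analysed item by item as categorical data. The instrument (Addendum 8.1) is not in the documents. This stands, and makes the test point conditional. The missing summary of change does not depend on it.

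A second reply is that power has little bearing on a feasibility study that makes no power claim, and that the choice is immaterial at the only effect the plan cites. This also stands and limits the weight of the point. It does not remove the case for an estimate, which is what a pilot is for. It is also fair that a plan silent on the estimate does not show that only a p-value would be reported: section 3.2.5 gives before and after percentages next to its p-value.

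A reader might infer more than the documents support:
- That the Friedman test is wrong or biased here. It is a usable test of direction; the chi-square version is slightly liberal without ties.
- That the LKS alone lacks a confidence interval. None of the outcomes in 3.2.6 has one. The contrast is only that the DCS and fidelity have a named median and the LKS has no summary of change.
- That binary items are certain to be handled efficiently under CMH. They lose nothing if the test is stratified by participant, but the plan does not say that it is.

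**Conclusion.** The point holds in a limited form and is minor. If the LKS gives a non-categorical score, the named test discards the size of each change. The cost is roughly 2 to 11 points of power for small to moderate gains on a bounded score, and nothing for gains like 69% to 93%. Those figures rest on n=50, a two-sided 5% level and assumed score distributions. Whatever the data type, 3.2.6 names no summary of the LKS change and no interval, although Aim 2 is meant to give preliminary evidence of effectiveness. This is a loss of information, not a bias, in a feasibility study with no power claim.

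**What to change.** In section 3.2.6:
- For any LKS total or percent-correct score, replace Friedman with one matched test and interval, fixed before the data are seen. The paired t test with the mean paired change and its 95% CI is preferable. The rank alternative is the Wilcoxon signed-rank test with the Hodges-Lehmann shift and its CI.
- Do not combine Wilcoxon with a t-type interval for the mean, since the two target different quantities when changes are skewed. On a short item score the mean is also more informative: in the one-item example above the Hodges-Lehmann shift is 0 (95% CI 0 to 1), against a mean of 0.28.
- For categorical items, state that CMH is stratified by participant (McNemar for correct/incorrect), and report the paired difference in percent correct with its 95% CI.

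If only one change is made, it should be the estimate with its interval. The cost is a few sentences and no new data. The downsides are that paired t is less powerful than the sign statistic for heavy-tailed changes, which are unlikely on a short bounded score, and that Wilcoxon relies on roughly symmetric changes.
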